	
Summary of PD response, in terms of number (%) of subjects, will be provided. IPA as measured by VerifyNow® will also be summarized as a continuous variable.
 
Supportive/sensitivity analyses
 
Consistency across the following subgroups will be assessed by repeating the primary endpoint analysis, assuming relevant number of subjects:
 
• Age: < 55 vs \geq 55 years• Body mass index: < 25.0 vs (\geq 25.0 and < 30.0) vs \geq 30.0 kg/m^2• Sex: male vs female• Diabetes mellitus at baseline: yes vs no• Chronic kidney disease: yes vs no 
Additional analyses of the supportive PD endpoint (light transmission aggregometry-based PD response) will be conducted using the same approach as described for the primary PD analysis.
 
Sample size
 
The primary objective is to assess the effectiveness of ACT-246475 to allow subjects to achieve a predefined PD response; therefore, the sample size provided is sufficient to sequentially demonstrate that at least 1 of the 2 ACT-246475 doses has a higher response rate than placebo and that this response rate is greater than 70%.
 
The sample size required for demonstrating a difference to placebo, based on an overall type I error of 0.05 (2-sided), adjusted for multiplicity using a Bonferroni method to 0.025 for each comparison, a power of 90%, a response rate of 50% under H_0 (placebo) and 75% under H_1 is 96 per arm.
 
The sample size required to demonstrate that the response rate is different from 70% is based on a 2-sided type I error of 0.025, a power of 90%; and the assumptions of a response rate of 70% under H_0 and 85% under H_1 is 98 per arm.
 
The study should include at least 98 subjects in each treatment arm, and assuming a rate of drop-out or non-evaluable data of

--	---

	about 10%, 108 subjects should be included in each arm, giving a total of 324 subjects enrolled in the study.

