10.3.2.1 Hypotheses and statistical model

The primary goal is to determine that the proportion p of subjects receiving a dose of ACT-246475, who achieve the PD response as measured by VerifyNow®, is statistically greater than 70%.

In order to achieve this objective, the testing strategy will consider a sequential approach demonstrate a statistically significant difference between the control arm (placebo) and at least 1 of the active arms, then to confirm that the observed response rate (P_r) in the same active arm is statistically significantly greater than the predefined response rate.

The comparison of each of the 2 active treatment arms will be conducted vs placebo, with the following hypotheses:

$$H_{p0HD}: p_{placebo} = p_{HD}$$

vs

$$H_{p1HD}: p_{placebo} \neq p_{HD}$$

AND

$$H_{p0LD}: p_{placebo} = p_{LD}$$

vs

$$H_{p1LD}: p_{placebo} \neq p_{LD}$$

Where, $p_{placebo}$ is the proportion of responders in Placebo arm, p_{HD} is the proportion of responders in the ACT-246475 16 mg arm, and p_{LD} is the proportion of responders in the ACT-246475 8 mg arm.

The 2 null hypotheses will be tested for each dose by a 2-sided z-test at an overall significance level (alpha) of 0.05 adjusted for multiplicity using the Bonferroni method, i.e., 0.025 for each comparison.

Assuming that either H_{p0HD} , or H_{p0LD} , or both are rejected, then the following hypotheses will be tested for each of the active doses that were statistically significantly different from placebo:

$$H_0: P_{\text{responders}} = 0.70$$

vs

$$H_1: P_{\text{responders}} > 0.70$$

The null hypothesis will be tested for each dose by a 1-sided z-test at an overall significance level (alpha) of 0.05 adjusted for multiplicity using the Bonferroni method, i.e., 0.025 for each comparison.

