10.5 Sample size

The sample size is based on the primary PD endpoint, which is the proportion of subjects achieving a predefined PD response as measured by VerifyNow®. The computation of the sample size was performed using the East 6.0 software (version 6.4.0.1, 30 Aug. 2016) from Cytel.

This study includes 3 treatment arms, 2 active arms (ACT-246475 8 mg and 16 mg) and a placebo arm comprising the 2 dose-matching placebo groups.

The primary objective is to assess the effectiveness of ACT-246475 to allow subjects to achieve a predefined PD response, therefore the sample size will be provided in order to reach the necessary power to sequentially demonstrate that at least 1 of the 2 doses has a higher response rate than placebo and that this response rate is statistically significantly greater than the proportion of responders under H_0 .

The sample size required for demonstrating a difference to placebo is based on an overall alpha of 0.05 (2-sided), adjusted for multiplicity using a Bonferroni method to 0.025 for each comparison, and a power of 0.9; the assumptions related to response rate under the null and alternative hypotheses are reported in the table below:

Proportion of responders under H_0 (placebo)	Proportion of responders under H_1 (active)	Number of subjects (total)	Number of subjects (per arm)
50%	75% (odds ratio of 3)	288	96

The sample size required to demonstrate that the achieved response rate is different from 70% is based on a 2-sided type I error (alpha) of 0.025, and a power of 0.9; the assumptions related to response rate under the null and alternative hypotheses, are reported in the table below:

Proportion of responders under H_0	Proportion of responders under H_1	Number of subjects (total for the 2 active arms)	Number of subjects (per arm)
70%	85%	196	98

Therefore the study should include at least 98 subjects evaluable for the primary PD endpoint in each treatment arm. Assuming a rate of drop-out or non-evaluable data of about 10%, each arm will include 108 subjects leading to a total for the study of 324 subjects.

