6.8.1.2 Analysis

The analyses described in this section consider the primary endpoint, i.e., PD response. Sensitivity analysis of the other estimands are described in the sensitivity analyses section.

Unless stated otherwise, all analyses will be conducted on the FAS.

The study is designed to demonstrate that at least one dose of ACT-246475 enables a large proportion (a target of 85%) of the randomized subjects to achieve a clinically meaningful level of IPA, defined as a PRU < 100.

Hypotheses and statistical model

The primary goal is to determine that the proportion (p) of subjects receiving a dose of ACT-246475, who achieve the PD response as measured by VerifyNow®, is statistically greater than 70%.

To achieve this objective, the testing strategy considers a sequential approach to demonstrate a statistically significant difference between the control arm (placebo) and at least 1 of the active arms, then to confirm that the observed response rate (P_r) in the same active arm is significantly statistically greater than the predefined response rate.

The comparison of each of the 2 active treatment arms will be conducted vs placebo, with the following hypotheses:

$$H_{p0_{HD}}: p_{placebo} = p_{HD} \quad \text{vs} \quad H_{p1_{HD}}: p_{placebo} \neq p_{HD}$$

$$H_{p0_{LD}}: p_{placebo} = p_{LD} \quad \text{vs} \quad H_{p1_{LD}}: p_{placebo} \neq p_{LD}$$

Where, $p_{placebo}$ is the proportion of responders in placebo arm, p_{HD} is the proportion of responders in the ACT-246475 16 mg arm and p_{LD} is the proportion of responders in the ACT-246475 8 mg arm.

Assuming either $H_{p0_{HD}}$, or $H_{p0_{LD}}$, or both are rejected, then the following hypotheses will be tested for each of the active doses that was statistically significantly different from placebo:

$$H_0: P_{responders} = 0.70 \quad \text{vs} \quad H_1: P_{responders} = 0.85.$$

Main analysis

The first set of null hypotheses ($H_{p0_{HD}}$ and $H_{p0_{LD}}$) will be tested each using a 2-sided z-test at an overall significance level (alpha) of 0.025, corresponding to an overall alpha level of 0.05 adjusted for multiplicity using the Bonferroni method.

Each of the second null hypotheses ($H_{0_{HD}}$ and $H_{0_{LD}}$) will be tested by a 1-sided z-test at an overall significance level (alpha) of 0.05 adjusted for multiplicity using the Bonferroni method, i.e., 0.025 for each comparison.

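### The 1-sided z-test against 70% does not guarantee its stated 0.025 level: exact size is 0.0280 per dose at n = 108, and at other n it depends on an unspecified standard error

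*SAP*

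**What the plan says.** The primary analysis has two steps. Each dose is first compared with placebo by a 2-sided z-test at 0.025. The test against 70% then follows: in the SAP's words, the second-step hypotheses "will be tested for each of the active doses that was statistically significantly different from placebo". Under Protocol 10.3.1 the study is positive if both steps reject for at least one dose.

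For the second step, SAP 6.8.1.2 states that each null hypothesis "will be tested by a 1-sided z-test at an overall significance level (alpha) of 0.05 adjusted for multiplicity using the Bonferroni method", giving 0.025 per comparison. Protocol 10.3.2.1 agrees: the null hypothesis is "tested for each dose by a 1-sided z-test at an overall significance level" of 0.05, split in the same way. Neither text says whether the standard error uses 0.70 or the observed proportion, and neither mentions a continuity correction or an exact test. SAP 6.8.1.2 also promises a 95% CI for the response proportion without naming a method.

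On size, Protocol 10.5 asks for at least 98 evaluable subjects per arm and then states that "each arm will include 108 subjects leading to a total for the study of 324 subjects". The sample size for the test against 70% "is based on a 2-sided type I error (alpha) of 0.025, and a power of 0.9".

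On the denominator, Protocol 10.3.2.2 counts subjects with an undeterminable response as non-responders in the main analysis, and the algorithm in SAP 6.8.1.1 does the same by sending every other case to NO. SAP 6.8.3 leaves such subjects out of the main-analysis response rate and counts them as non-responders only in the sensitivity analysis.

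**The concern.** The second step carries the main claim of the study, since exceeding 70% is described as the primary goal. The plan attaches a formal error rate to it: 0.025 per dose and 0.05 over the two doses. A one-sample z-test on a count of about 100 has only an approximate level, because the count moves in whole subjects. Whether the real level lies below or above 0.025 depends on n and on the standard error, and the plan fixes neither.

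At stake is a result on the boundary. With 85 responders of 108 the z-test declares success, while the exact one-sided p-value is 0.0280. A positive declaration resting on that count could be challenged on the stated alpha.

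**Working it through.** **Inputs.** p0 = 0.70, target 0.85, 1-sided 0.025 per dose (SAP 6.8.1.2, Protocol 10.3.2.1); 98 evaluable and 108 enrolled per arm, planning placebo response 50% (Protocol 10.5).

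**The plan's own figures.** With the null variance in the usual formula and 0.0125 in the upper tail:

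n = [(2.2414 × √(0.70 × 0.30) + 1.2816 × √(0.85 × 0.15)) / 0.15]² = 97.98, so 98.

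The increase for about 10% loss is 98 × 1.1 = 107.8, so 108. Both planned figures are reproduced.

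**Cut-off and exact size at n = 108.** The test rejects when z ≥ 1.96.

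- 84 responders (0.7778): z = 0.0778 / √(0.21/108) = 1.764 with the null SE, and 1.944 with the sample SE. Not rejected.
- 85 responders (0.7870): z = 1.974 with the null SE, and 2.209 with the sample SE. Rejected.

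Both forms reject from 85, and P(X ≥ 85 | n = 108, p = 0.70) = 0.0280.

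**Two doses.** Without the placebo comparison, the chance of at least one false rejection is 1 − (1 − 0.0280)² = 0.0552. The placebo comparison barely changes this at the planning value. For example, 85 of 108 against 54 of 108 gives a pooled proportion of 139/216 = 0.6435 and z = 0.2870 / √(0.6435 × 0.3565 × 2/108) = 4.40, well past the 2.2414 needed. Enumerating both steps with a shared placebo arm of 108 and both doses at a true 70%:

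| True placebo response | At least one dose falsely positive |
|---|---|
| 50% or lower | 0.055 |
| 60% | 0.050 |
| 70% | 0.012 |

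**Dependence on n and on the standard error.** Exact size per dose, with the cut-off in brackets:

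| n | z-test, null SE | z-test, sample SE | Exact binomial |
|---|---|---|---|
| 97 | 0.0254 (77) | 0.0430 (76) | 0.0142 (78) |
| 98 | 0.0220 (78) | 0.0377 (77) | 0.0220 (78) |
| 100 | 0.0288 (79) | 0.0288 (79) | 0.0165 (80) |
| 101 | 0.0251 (80) | 0.0422 (79) | 0.0142 (81) |
| 104 | 0.0284 (82) | 0.0284 (82) | 0.0164 (83) |
| 107 | 0.0188 (85) | 0.0319 (84) | 0.0188 (85) |
| 108 | 0.0280 (85) | 0.0280 (85) | 0.0163 (86) |
| 109 | 0.0245 (86) | 0.0404 (85) | 0.0245 (86) |

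Over n = 90 to 112, the null-SE form exceeds 0.025 only at 93, 97, 100, 101, 104, 108 and 112. The sample-SE form exceeds it at every n, ranging from 0.0275 to 0.044. The exact test differs from the null-SE z-test only at those n where the latter is above 0.025.

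**Power at a true 85%.** At n = 108: z-test 0.971, exact test 0.950. At n = 98: the exact test and the null-SE z-test are the same rule, 0.945. The lowest exact power for n = 90 to 112 is 0.903, at n = 93.

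**The case against.** The case against pressing this is fair in several respects.

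- *It is one value of n.* With the null SE, the level holds at 7 of the 11 values from 98 to 108, including the planned evaluable 98; one subject fewer than 108 brings the size to 0.0188. A reader might infer that the z-test inflates type I error throughout. The documents do not support that: with the null SE the pattern is binomial saw-tooth, and enrolment is only approximately 324. This limits the point, but it does not protect the sample-SE form, which the SAP equally allows.
- *A reader might put the two-dose error at 0.056 whatever happens on placebo.* That figure is the Bonferroni sum 2 × 0.0280. The probability of at least one false positive is 0.055, and only at a placebo response of 50% or lower; it falls to the stated 0.05 at 60% and well below it at 70%.
- *The sample size used a stricter level.* With 0.0125 in the upper tail, the null-SE z-test at n = 108 would reject from 87, with size 0.0090, and the excess would vanish. But the analysis text in both documents prescribes 1-sided 0.025, and that is the rule that will be run.
- *The remedy overshoots.* At n = 108 the exact test runs at 0.0163, further below 0.025 than the z-test is above it. Preferring a guaranteed level to an approximate one is a choice, and the study is described as exploratory Phase 2. This stands as an argument for minor severity. It does not remove the mismatch, because the protocol itself adopted formal hypotheses, Bonferroni control and a declared-positive rule.

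**Conclusion.** The point holds in limited form, at minor severity. As written, the test against 70% does not guarantee 0.025 per dose. At exactly 108 per arm the exact size is 0.0280 under either standard error, an excess of 0.003, and the two-dose error is about 0.055 if placebo response is 50% or lower. At 98 the level is met with the null SE (0.0220) and missed with the sample SE (0.0377), so the missing formula matters more than the excess at 108.

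Which n applies cannot be settled from the documents: Protocol 10.3.2.2 and SAP 6.8.1.1 point to about 108, and SAP 6.8.3 points to about 98 if the planned 10% loss occurs.

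These figures assume an uncorrected z-test at 1.96, independent binomial responses within each arm, and both doses exactly at 70%. At 108 per arm the z-test and the exact test reach different conclusions for a dose only if exactly 85 subjects respond.

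**What to change.** In SAP 6.8.1.2, replace the one-sample z-test by the exact one-sided binomial test of 70% at 0.025 per dose, with the cut-off computed for the actual n: 86 of 108, or 78 of 98, the latter unchanged from the null-SE z-test. For the 95% CI of the response proportion, name the Clopper-Pearson interval; its lower limit lies above 70% exactly when this test rejects at 0.025, so test and interval agree. Reconcile SAP 6.8.3 with SAP 6.8.1.1 and Protocol 10.3.2.2, so that the denominator is fixed before unblinding.

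The cost is SAP wording, with no change to design or sample size. At 108 per arm, power at 85% falls from 0.971 to 0.950, and the two-dose error becomes 0.032 at a placebo response of 50%. For n = 90 to 112 the power of the test against 70% stays above the planned 90%.

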3 OVERALL STUDY DESIGN AND PLAN

3.1 Study design

This is a prospective, multi-national, multi-center, double-blind, randomized, placebo-controlled, parallel-group, Phase 2, exploratory study of a single s.c. administration of ACT-246475, at 2 different dose levels, in subjects with stable CAD receiving conventional background therapy (e.g., acetylsalicylic acid, P2Y₁₂ receptor antagonists, etc.).

Approximately 324 adult subjects with stable CAD will be randomized into 1 of the 8 combinations of the treatment, dose, and injection site using a 2:2:2:2:1:1:1:1 ratio as described in [Figure 1](#).

Figure 1 Randomization scheme

Each subject will receive a single s.c. administration of either 8 mg ACT-246475, 16 mg ACT-246475 or matching placebo, either in the thigh or in the abdomen.

Treatment group allocation will be stratified based on baseline platelet reactivity value (expressed as P2Y₁₂ reaction units [PRU]) measured on Day 1 by the VerifyNow® assay before ACT-246475 injection, considering the 3 following categories: high reactivity (PRU > 250), medium reactivity (150 ≤ PRU ≤ 250), and low reactivity (PRU < 150).

No interim analysis is planned for this study.

The study will be conducted at approximately 20 sites and in 5–10 countries (recruitment will be competitive across sites). The list of sites including the name and title of the investigators who are responsible for conducting the trial, and the address and telephone numbers of the trial sites will be filed in the Trial Master File (TMF).

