5.1.3 Study treatment assignment and dispensing

5.1.3.1 Study treatment assignment

At Visit 2, after having verified that the subject meets all inclusion criteria and none of the exclusion criteria, and after performing the pre-dose VerifyNow® assessments, the platelet aggregation technician will provide the PRU stratification group to the person who will randomize the subject using the Interactive Response Technology (IRT) system. The IRT will assign a randomization number to the subject and will assign the treatment kit number as well as the dose and injection site, which matches the treatment arm assigned by the randomization list to the randomization number.

The randomization list will be generated by an independent Contract Research Organization (CRO).

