- AE, Adverse event; BP, Blood pressure; ECG, Electrocardiogram; EOS, End-of-Study; INR, International normalized ratio; LTA, Light transmission aggregometry; PK, Pharmacokinetics; s.c., Subcutaneous; SAE, Serious adverse event.

Table 3 Time points of main study assessments

PERIOD	TREATMENT PERIOD										
	Visit	Visit 2 (Randomization ^a)									Visit 3
		Day 1 ^b									
Time point	Pre-dose	0 min	15 min ±1 min	30 min ±2 min	1h ±3 min	2h ±6 min	4h ±12 min	8h ±24 min	24h ±2h		
Vital signs (BP, Pulse rate)	X			X	X	X	X	X	X		
12-lead ECG	X					X ^d				X	
PK Blood sampling	X		X	X	X	X	X	X	X		
VerifyNow®	X ^a		X	X	X	X	X	X	X		
LTA (for patients ≥ 50.0 kg only) ^c	X ^a			X	X	X					
s.c. injection (ACT-246475 or placebo)		X									

- a. Randomization will be performed after pre-dose blood sampling for VerifyNow® and LTA assessments on Day 1. The dose allocated (8 mg or 16 mg) must not be communicated to the subject.
- b. The following order of assessments is to be followed (as applicable): PK sample (to be collected at the protocol-defined time point), VerifyNow® sample, LTA sample.
- c. No blood samples are to be collected for LTA assays for subjects with body weight < 50.0 kg (110 lbs), only VerifyNow® assays are performed for these subjects.
- d. Time window for performing the post-dose ECG is ±30 min.

BP, Blood pressure; ECG, Electrocardiogram; EOS, End-of-Study; LTA, Light transmission aggregometry; PK, Pharmacokinetics; s.c., Subcutaneous.

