10.3.2.3 Main analysis

The primary statistical analysis will be performed on the FAS population for each dose level.

The first set of null hypotheses (H_{p0HD} and H_{p0LD}) will be tested for each dose by a 2-sided z-test at an overall significance level (alpha) of 0.05 adjusted for multiplicity using the Bonferroni method, i.e., 0.025 for each comparison.

The second null hypothesis (H_0) will be tested for each dose by a 1-sided z-test. The estimated proportion of responders in each arm and the corresponding 95% CI will be provided.

A longitudinal analysis of the treatment effect, from start of treatment up to 8 h after injection, on platelet reactivity as measured by VerifyNow®, i.e., PRU value, will be performed using a mixed model with PRU as the dependent variable, subject as a random factor, and treatment (8 mg, 16 mg, and placebo), injection site (abdomen, thigh), PRU level at randomization (stratification levels), age (continuous), gender (male, female), and assessment time (continuous) as fixed factors. The model will also include (treatment \times injection site) as an interaction term to assess consistency of treatment effect across injection sites.

A logistic regression analysis of the PD response will be performed using the same factor as covariates.

Summary of PD response, in terms of number (%) of subjects, will be provided. IPA as measured by VerifyNow® will also be summarized as a continuous parameter.

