The estimated proportion of responders and the corresponding 95% CI will be provided overall and by injection site, for each treatment arm.

A logistic regression analysis of the PD response will be performed to test for treatment effect (8 mg, 16 mg, and placebo) using the following covariates: injection site (abdomen, thigh), PRU level at randomization (stratification levels), age (continuous), sex (male, female), and assessment time (minutes) as continuous.

A longitudinal analysis of the treatment effect, from start of treatment up to 8 hours after injection, on platelet reactivity as measured by VerifyNow®, i.e., PRU value, will be performed using a mixed model with PRU as the dependent variable, subject as a random factor, and treatment (8 mg, 16 mg, and placebo), injection site (abdomen, thigh), PRU level at randomization (stratification levels), age (continuous), sex (male, female), and assessment time (minutes) as fixed factors. The model will also include

(treatment \times injection site) as an interaction term to assess consistency of treatment effect across injection sites.

IPA as measured by VerifyNow® will also be summarized at each time point as a continuous parameter.

The evolution of PRU values over time will be described using box-and-whisker plots, visualizing mean, median, interquartile ranges, SD, and outliers.

Assuming a treatment \times injection site interaction, summary and graphical analyses described above will be repeated by site injection sub-group.

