6.8.2.2 Analyses

Summary statistics will be provided for all secondary PD endpoints variables, by time point, and individual data will be listed.

The variables' extent of aggregation, absolute PRU, IPA, and FPA will be analyzed similarly to the longitudinal analysis described for the primary PD endpoint in Section 6.8.1.2, and will use the same factors.

A logistics regression model will be used to assess the treatment effect relative to placebo of each ACT-246475 dose on subject platelet aggregation status 8 hours after study drug administration. The factor considered in addition to the treatment group, will include injection site (abdomen, thigh), PRU level at randomization (stratification levels), age (continuous), and sex (male, female) as fixed factors. The model will also include (treatment \times injection site) as an interaction term to assess consistency of treatment effect across injection sites.

Proportion of subject by platelet aggregation status 8 hours after study drug administration will be plotted as bar charts. Additional graphs will be provided by injection site.

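### The supportive longitudinal PRU, MPA and FPA models adjust for baseline reactivity only by a three-level PRU category, which gives up some precision against placebo

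*SAP*

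**What the plan says.** Protocol 10.3.2.3 plans a "mixed model with PRU as the dependent variable, subject as a random factor". Its fixed part holds treatment, injection site, treatment by injection site, and "PRU level at randomization (stratification levels), age (continuous), gender (male, female), and assessment time (continuous) as fixed factors". SAP 6.8.1.2 repeats the list with time in minutes: "PRU level at randomization (stratification levels), age (continuous), sex (male, female), and assessment time (minutes) as fixed factors". The category is the randomisation stratum, with cut points at 150 and 250 PRU (protocol 3.1).

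For the other continuous outcomes, which include MPA and FPA, SAP 6.8.2.2 says they "will be analyzed similarly to the longitudinal analysis described for the primary PD endpoint in Section 6.8.1.2, and will use the same factors". Neither document adds a continuous baseline covariate or a change-from-baseline version of these models.

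The measured values are in hand. Protocol 5.1.3.1 has the stratum reported only "after performing the pre-dose VerifyNow® assessments, the platelet aggregation technician will provide the PRU stratification group", so a correctly randomised subject has a pre-dose PRU. The footnote to protocol Table 3 says: "Randomization will be performed after pre-dose blood sampling for VerifyNow® and LTA assessments on Day 1". LTA is limited to subjects of at least 50 kg. SAP 6.8.2.1 already derives a baseline MPA, but only as the denominator of IPA-M.

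**The concern.** Pre-dose PRUs of 5 and 149 get the same adjustment. If untreated subjects keep roughly the reactivity they started with, the spread of baselines inside a stratum stays in the error term although it could be removed. For MPA and FPA the gap is wider, because a VerifyNow category is only an indirect measure of baseline LTA.

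The SAP itself treats position within the lowest stratum as informative. Section 11.1.1 redefines the 8 h variable because some subjects start below 100 PRU.

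At stake is the precision of the planned continuous estimates of effect against placebo, and of the treatment by injection site term. SAP 6.8.1.2 uses that term to judge consistency across sites and to decide whether summaries and graphs are repeated by site. The protocol's purpose statement (1.4) looks to these data for later dose selection.

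**Working it through.** **1. The plan's own figures.** The documents state no SD, correlation or power for the longitudinal models. Their sample sizes concern the binary PD response, and they reproduce:
- Test against 70%: ((2.241 × √0.21 + 1.282 × √0.1275) / 0.15)² = 98.
- Against placebo, by the log odds ratio: (2.241 + 1.282)² × (1/0.25 + 1/0.1875) / (ln 3)² = 96.
- Inflation: 98 × 1.10 = 108 per arm.

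None of these depends on the covariates discussed here. Everything below rests on assumed inputs.

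**2. How much baseline variance the category keeps (R²).**
- Uniform 50-350: variance within a stratum is 100²/12 = 833 and total variance is 300²/12 = 7,500. The share lost is 833/7,500 = 0.111.
- Normal, mean 190, SD 70: share lost 0.198.
- Normal, mean 150-220, SD 40-80: 63-81% kept, so 19-37% lost.

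**3. Effect on PRU if all arms track baseline equally.** Let ρ be the correlation of pre-dose PRU with the subject's post-dose mean. Adding the continuous value multiplies the residual variance by (1 − ρ²)/(1 − ρ²R²). With R² = 0.75:

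| ρ | Variance cut | SE cut |
|---|---|---|
| 0.3 | 2% | 1% |
| 0.5 | 8% | 4% |
| 0.7 | 19% | 10% |
| 0.8 | 31% | 17% |
| 0.9 | 52% | 30% |

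For example, at ρ = 0.8: 0.36/(1 − 0.64 × 0.75) = 0.36/0.52 = 0.692, and √0.692 = 0.832.

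**4. Effect on PRU if active arms track baseline less.** Simulation with 108 per arm and stratified allocation, 2,000 trials per row. It models subject means, which for balanced time points is equivalent to the random-intercept contrast. Baseline and placebo have mean 200 and SD 60; the 8 mg and 16 mg means are 60 and 30. One common baseline slope is added. Entries are the SD of the estimate across trials, category only → category plus continuous value.

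| Placebo ρ | Active ρ (active SD) | 8 mg − placebo | 16 mg − 8 mg |
|---|---|---|---|
| 0.8 | 0.8 (60) | 5.75 → 4.89 (−15%) | 5.79 → 4.94 |
| 0.9 | 0.5 (40) | 5.19 → 4.77 (−8%) | 4.94 → 4.89 |
| 0.8 | 0.3 (40) | 5.83 → 5.53 (−5%) | 5.28 → 5.30 |
| 0.8 | 0 (30) | 5.50 → 5.29 (−4%) | 4.01 → 4.12 (+3%) |
| 0.5 | 0.2 (40) | 6.48 → 6.40 (−1%) | 5.34 → 5.32 |

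**5. MPA and FPA.** Let q be the correlation of baseline MPA with baseline PRU. The category then explains only (ρq)²R² of the outcome variance. At q = 0.7, ρ = 0.8 and R² = 0.75 this is 0.56² × 0.75 = 0.235. The variance ratio is 0.36/0.765 = 0.471, an SE cut of 31%. Simulated cuts in the active-placebo SE, with q = 0.7:
- ρ = 0.8 in all arms: 31%.
- Placebo 0.8, active 0.3: 12%.
- Placebo 0.8, active 0: 8%. Here the SD of 16 mg versus 8 mg rose by about 9%.
- Placebo 0.5, active 0.2: 4%.

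**6. One slope or one per arm.** Further PRU simulations used 108 per arm and assumed slopes, with active arms barely following baseline. One common slope cut the SD of 16 mg versus placebo by about 3-10% but raised that of 16 mg versus 8 mg by about 3-12%. Thigh versus abdomen within 16 mg also lost 1-11%. With a baseline by treatment interaction, 16 mg versus 8 mg stayed level or better, and 16 mg versus placebo improved by about 6-13%.

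**The case against.** The planned model is valid as it stands. It respects the stratified randomisation, the cut points have a stated rationale (protocol 3.2), and the category keeps most of the baseline variance. Neither bias nor type I error is in question. The model is supportive: trial success rests on z-tests of a binary response, in a study labelled exploratory. If the drug effect is as large as assumed above (140 PRU, against an SD of the estimate of about 5-6), a gain of a few percent changes no verdict. A single added slope can also harm the dose comparison. All of this stands. It limits the importance of the point and shapes the fix, but it does not supply the missing covariate.

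A reader might infer three stronger things that the documents do not support:
- That every contrast would gain. The gain comes from arms that follow baseline. Active subjects are meant to fall below 100 PRU and may follow it weakly, so dose-to-dose and within-dose site contrasts may gain nothing.
- That precision at 8 h is lost in this model. It has no treatment by time term and gives no 8 h contrast. Formal inference at 8 h is a separate logistic regression on a binary status (SAP 6.8.2.2).
- That the primary conclusion is at risk. The z-tests use no covariates.

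The SAP does not say whether the pre-dose value is itself a response in the period from start of treatment to 8 h. On either reading it is not a covariate.

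**Conclusion.** The point holds as a matter of efficiency in supportive models. PRU is adjusted for a coarse version of a value that was measured. MPA and FPA are adjusted for a category from another assay and not for their own baseline. The loss falls mainly on active-placebo contrasts and on the treatment by injection site interaction, which also involves placebo. The interaction was not sized separately here.

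On the assumptions shown, the loss is about 1-15% of the SE of the active-placebo PRU difference, reaching 30% by formula if all arms track baseline at ρ = 0.9. For MPA and FPA it is about 4-31%. The direction for active versus placebo was the same in every scenario. The size is not known, because it depends on SDs and correlations that the documents do not give.

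The confirmatory tests, their alpha and the 324-subject sample size are untouched, and the active-placebo conclusion is unlikely to change. The change is worth making because it is cheap, not because the plan fails without it.

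**What to change.** In SAP 6.8.1.2, keep the stratum and add to the longitudinal PRU model the mean-centred continuous pre-dose PRU and its interaction with treatment. In SAP 6.8.2.2, add the subject's own centred pre-dose MPA to the MPA model and pre-dose FPA to the FPA model, each with the same interaction. Centring makes the treatment coefficients refer to a subject of average baseline. The interaction guards against the loss for 16 mg versus 8 mg shown above.

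Name the baseline as the last value before injection, as in SAP 10.2.2, because the general rule in protocol 10.2 averages the last two screening-phase values. State that the pre-dose value is a covariate and not also a response.

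The cost is three parameters per model (one slope and two interaction terms) and no new data. The LTA models remain limited to subjects of at least 50 kg.
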